## SUMMARY OF CHANGES

GT0918-US-1002 Protocol Version 5.0, changes below have been made to respond to questions and comments from investigational sites.

1. To add additional 6 cycles to current treatment duration to extend the treatment duration to 30 cycles, per subject's willing and investigators' discretion.
2. Disease Assessment scans (CT or MRI or bone scan) is added with Cycle 27 D28 and Cycle 30 D28.
3. Complete Physical Exam is added with Cycle 27 D28 and Cycle 30 D28
4. Abbreviated Physical Exam is added with Cycle 26 Day 1, Cycle 27 Day1, Cycle 29 Day 1, Cycle 30 Day 1.
5. 12-lead ECG is added with Cycle 25 Day 1 and Cycle 28 Day 1.
6. Exploratory markers test is added with Cycle 25 Day 1 and Cycle 28 Day 1.
7. Change Kintor Legal address is updated to [name]

Suzhou Kintor Pharmaceutical, Inc.  
Protocol#: GT0918-US-1002

Proxalutamide (GT0918)

## 1 SYNOPSIS (EXPANDED/PHASE II)

Name of Sponsor/Company: Suzhou Kintor Pharmaceutical, Inc.
Name of Investigational Product: Proxalutamide (GT0918)
Title of Study:  An Expanded/Phase II, Multi-Center, Randomized, Open-Label Study to Evaluate the Safety and Tolerability of Proxalutamide (GT0918) in Subjects with Metastatic Hormone Sensitive Prostate Cancer (mHSPC) or Metastatic Castrate Resistant Prostate Cancer (mCRPC) who Failed Either Abiraterone or Enzalutamide
Study period:  Date first subject enrolled: 2Q2019
Phase of development (2nd stage): Expanded/Phase II
Objectives (Expanded/Phase II):

Primary:
 
 
• Evaluate the safety and tolerability of GT0918 in subjects with mHSPC or mCRPC who failed either abiraterone or enzalutamide treatment and determine the Recommendation Phase II Dose (RP2D) for other Phase II or III studies.
 
 
Secondary:
 
 
• To evaluate radiographic progression-free survival (rPFS)
 
• To evaluate objective response rate
 
• To evaluate time to radiographic progression
 
• To evaluate Prostate Surface Antigen (PSA) 50% decline and maximum change at 12 weeks
 
• To evaluate PSA doubling time (PSA DT)
 
• To evaluate the time to PSA progression
 
• To identify exploratory biomarkers to characterize androgen receptor (AR) inhibition and/or down-regulation by GT0918
 

Study Design (Expanded/Phase II):  This study is an open-label, randomized, expanded/phase II study in subjects with mHSPC or mCRPC who progressed after either abiraterone or enzalutamide treatment. All subjects will be randomized to take 400 mg or 500 mg of GT0918 by oral administration once daily on an empty stomach (2-3 hours after a meal) for initial treatment of 6 months. Randomization of subjects will be stratified by prior therapy (abiraterone or enzalutamide).  Subjects will continue treatment with GT0918 for up to 24 additional cycles (total up to 30 cycles) at their assigned dose on an empty stomach until disease progression, intolerable toxicities/adverse events

Suzhou Kintor Pharmaceutical, Inc.  
Protocol#: GT0918-US-1002

Proxalutamide (GT0918)

(AEs), or withdrawn consent. Subjects will end the study by completing the end of study (EOS) visit/assessment. The safety follow-up visit will occur 30 days after the last dose. Any subject with drug related AE or SAE will be followed until resolution or the subject's condition stabilizes, which comes first. The safety follow-up visit can be performed via phone or in clinic as required.

Disease progression will be assessed by three methods as follow over the duration of the study.

- 1) Clinical assessment
- 2) Biochemical (PSA) progression measured every 4 weeks
- 3) Radiographic progression by CT scan and/or bone progression by radionuclide bone scan every 12 weeks

Progressive disease will be considered on the occurrence of the first assessed progression event. For subjects with PSA progression may continue on study drug until radiographic and/or clinical progression, at the discretion of the Investigator and with the Medical Monitor agreement. A treatment diagram for the study is provided below in **Figure 1**.

**FIGURE 1**

**Biomarker Assessment:**

Subjects will have blood drawn for circulating tumor cells (CTC), ct-DNA and ct-RNA obtained at baseline and every 12 weeks during the study, all subjects on study drug over 20 weeks (over 3 time points) will be analyzed for these tumor biomarkers.

Suzhou Kintor Pharmaceutical, Inc.  
Protocol#: GT0918-US-1002

Proxalutamide (GT0918)

**Planned number of subjects:** 60 (30 subjects per treatment arm) as displayed in **Figure 1:**

ARM1: 400mg /day of GT0918

Group 1: Post enzalutamide (N=15)

Group 2: Post abiraterone (N=15)

ARM 2: 500 mg/day of GT0918

Group 1: Post enzalutamide (N=15)

Group 2: Post abiraterone (N=15)

**Study center(s):**

10 study centers located in the United States.

**Diagnosis and Inclusion/Exclusion criteria (expanded/phase II):**

Inclusion criteria:

1. Signed informed consent obtained prior to any study-related procedure being performed.
2. Subjects at least 18 years of age or older at the time of consent.
3. Subjects with histologically confirmed mHSPC or mCRPC who received abiraterone or enzalutamide for the hormonal treatment of 6 month or longer.
4. Subjects with mHSPC are required to have no prior ADT (androgen deprivation therapy) or orchiectomy. For mCRPC, ongoing androgen deprivation therapy with a luteinizing hormone-releasing hormone (LHRH) “super-agonist” or antagonist, or bilateral orchiectomy. Serum testosterone level is < 50 ng/dL (< 0.5 ng/mL, < 1.7 nmol/L) at screening.
5. Metastatic disease documented by computed tomography (CT)/magnetic resonance imaging (MRI) or bone scan.
6. Progressive disease despite hormonal treatment with abiraterone or enzalutamide for over 6 months (but not both). However, if either abiraterone or enzalutamide were used less than 3 months before discontinuation due to toxicity, the subject is eligible. Progressive disease is defined by 1 or more of the following criteria:
  - a. Subjects with a rising prostate specific antigen (PSA) value > 2 ng/mL in at least 2 measurements, at least 1 week apart. If the confirmatory PSA value is less than the screening PSA value, then an additional test for the rising PSA is required to document progression.
  - b. Subjects with measurable disease, progression defined by Response Evaluation Criteria in Solid Tumors (RECIST) 1.1 criteria
  - c. Subjects with metastatic bone disease, progression defined by 2 or more new lesions in a radionuclide bone scan.
7. ECOG performance status of 0-1
8. Screening blood counts of the following:
  - a. Absolute neutrophil count  $\geq$  1500/ $\mu$ L
  - b. Platelets  $\geq$  100,000/ $\mu$ L
  - c. Hemoglobin > 9 g/dL (if asymptomatic).
9. Screening chemistry values of the following:

- a. Alanine aminotransferase (ALT) and aspartate transaminase (AST)  $\leq 2.5 \times$  upper limit of the normal reference range (ULN)
- b. Total bilirubin  $\leq 2 \times$  ULN
- c. Creatinine  $\leq 1.5 \times$  ULN
- d. Albumin  $> 2.8 \text{ g/dL}$ .

10. At screening, life expectancy of at least 6 months.

11. Subjects whose partners are women of childbearing potential (WOCBP) must use an adequate method of birth control while on study drug and for at least 3 months after discontinuation of study drug.

12. Subject is willing and able to comply with all protocol required visits and assessments.

Exclusion criteria:

- 1. Discontinuation of enzalutamide or abiraterone less than 3 weeks prior to the start of study medication.
- 2. Prior chemotherapy and experimental therapy (Poly (ADP-ribose) polymerase (PARP) or checkpoint inhibitor)
- 3. Ongoing acute treatment-related toxicity associated with a previous therapy greater than grade 1 except for grade 2 alopecia or neuropathy.
- 4. History of impaired adrenal gland function (e.g., Addison's disease, Cushing's syndrome).
- 5. Known gastrointestinal disease or condition that affects the absorption of GT0918.
- 6. History of congestive heart failure New York Heart Association (NYHA) class III or IV or uncontrolled hypertension at screening.
- 7. History or family history of long QT syndrome, or ECG corrected QT interval equal to and over 500 ms (Common Terminology Criteria for Adverse Events (CTCAE) V 4.03 grade 2) at baseline.
- 8. History of other malignancy within the previous 3 years, except basal cell or squamous cell carcinoma, or non-muscle invasive bladder cancer.
- 9. Use of systemic glucocorticoid (e.g., prednisone, dexamethasone) within 14 days prior to the start of study medication. Inhaled or topical steroids are allowed.
- 10. Co-administration of CYP3A4 ligands that serve as substrates or induce or inhibit the enzyme (See Appendix 4 for the list of medications). If some medication needs to be used for the chronic illness, the medication shall be changed to another one that is not on the list or the dose should be reduced, at the discretion of the Investigator.
- 11. Prior use of any herbal products known to decrease PSA levels (e.g., PC-SPES or saw palmetto) within 30 days prior to the start of study medication.
- 12. Major surgery within 30 days prior to the start of study medication.
- 13. Blood transfusion (including blood products) within 1 week of screening.
- 14. Serious persistent infection within 14 days prior to the start of study medication.
- 15. Serious concurrent medical condition including CNS disorders.
- 16. Previous history of difficulty swallowing capsules or tablets.
- 17. Known hypersensitivity to GT0918 or its excipients (See Appendix 5 for drug details).

Suzhou Kintor Pharmaceutical, Inc.  
Protocol#: GT0918-US-1002

Proxalutamide (GT0918)

18. Any condition that, in the opinion of the investigator, would impair the subject's ability to comply with study procedures.

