Enzalutamide (Xtandi) has a higher antagonistic activity than bicalutamide in CRPC cells and effectively suppresses the activation, preventing AR transfer from then cytoplasm to the nucleus and from binding to DNA, ultimately achieving significant clinical efficacy for advanced castration-resistant prostate cancer. Enzalutamide has shown long half-life in subjects (3-13 days). When administered once a day, it will lead to serious drug accumulation, resulting in significant side effects, fatigue 34%, headache 12%, and some serious neurotoxicity, such as induced epilepsy of 1-2 %.

GT0918 is a new investigational second-generation androgen receptor antagonist with more specificity and activity in inhibiting androgen receptors; in particular, it can maintain a pure role of an antagonist because it does not activate the AR of CRPC cells compared to bicalutamide. As compared to enzalutamide, GT0918 has improvement in target potency as well as drug disposition properties. It is expected to reduce drug accumulation, which may reduce drug exposure in the CNS, therefore avoiding the CNS side effect such as seizure.

In addition, GT0918 demonstrates a dual mechanism of action in cell assays, i.e., highly effective in inhibiting AR as well as exhibiting pharmacological effects of inducing the down-regulation of AR expression; the mechanism that is not seen in bicalutamide and enzalutamide. Considering that over-expression of AR is one of the major mechanisms for generating resistance in castration therapy for prostate cancer, GT0918 could alleviate the resistance of castration therapy for prostate cancer because of the dual mechanism of action thus is expected to be a more effective and less toxic second-generation CRPC drug therapy. GT0918 may provide clinical benefits to some of the CRPC subjects who have developed resistance to enzalutamide or abiraterone treatments.

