## 7.2 Exclusion Criteria

- 1. Discontinuation of enzalutamide or abiraterone less than 3 weeks prior to the start of study medication.
- 2. Prior chemotherapy and experimental therapy (PARP or checkpoint inhibitor).
- 3. Ongoing acute treatment-related toxicity associated with a previous therapy greater than grade 1 except for grade 2 alopecia or neuropathy.
- 4. History of impaired adrenal gland function (e.g., Addison's disease, Cushing's syndrome).
- 5. Known gastrointestinal disease or condition that affects the absorption of GT0918.
- 6. History of congestive heart failure New York Heart Association (NYHA) class III or IV or uncontrolled hypertension at screening.

7. History or family history of long QT syndrome, or ECG corrected QT interval equal to and over 500 ms (CTCAE grade 2) at baseline.
8. History of other malignancy within the previous 3 years, except basal cell or squamous cell carcinoma, or non-muscle invasive bladder cancer.
9. Use of systemic glucocorticoid (e.g., prednisone, dexamethasone) within 14 days prior to the start of study medication. Inhaled or topical steroids are allowed.
10. Co-administration of CYP3A4 ligands that serve as substrates or induce or inhibit the enzyme. (See Appendix 4 of list of medications) If such medication needs to be used for the chronic illness, the medication shall be changed to another one that is not on the list or the dose should be reduced, at the discretion of the Investigator.
11. Prior use of any herbal products known to decrease PSA levels (e.g., PC-SPES or saw palmetto) within 30 days prior to the start of study medication.
12. Major surgery within 30 days prior to the start of study medication.
13. Blood transfusion (including blood products) within 1 week of screening.
14. Serious persistent infection within 14 days prior to the start of study medication.
15. Serious concurrent medical condition including CNS disorders.
16. Previous history of difficulty swallowing capsules.
17. Known hypersensitivity to GT0918 or its excipients (See Appendix 5 for drug details).
18. Any condition that, in the opinion of the investigator, would impair the subject's ability to comply with study procedures

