### 8.6.1 Permitted Treatment

- Full supportive care is to be administered per normal or routine practice at the study center. Concomitant anti-cancer therapy is not permitted. Palliative and supportive care for disease-related symptoms will be allowed to subjects in this study (e.g. bisphosphonates). However, subjects requiring palliative radiation anti-cancer therapy will be removed from the study.

- Subjects are required to continue the LHRH super-agonists/antagonists (if currently receiving this therapy prior to Cycle 1, Day 1) therapy unless having undergone bilateral orchiectomy.
- Standard therapies for concurrent medical conditions, such as if the subject is taking a regimen for pain control under physician supervision.
- Treatment for nausea, vomiting, and diarrhea, should they occur is allowed, using standard agents per institute's standard of practice. Tylenol and over the counter NSAIDs are also allowed.
- Subjects may receive antibiotics for infections that might occur

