### 8.6.2 Prohibited Treatment

- Glucocorticoids and herbs known to alter PSA levels (saw palmetto or PC-SPES)
- Any concurrent chemotherapy, radiotherapy, hormonal therapy (AR antagonists.), or immunotherapy
- Inducers or inhibitors of CYP3A4, or sensitive CYP3A substrates (detail see appendix 4)
- Other investigational agents

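### Other AR antagonists, other anticancer hormonal drugs, radiotherapy and some immunotherapy are prohibited from Day 1 but need no interval before it, so their after-effects can count as GT0918 activity in the within-arm secondary endpoints.

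*Combined protocol and SAP*

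**What the plan says.** The Synopsis and Section 7.2 carry the same rules on this point.

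- Exclusion 1 covers the two qualifying drugs: "Discontinuation of enzalutamide or abiraterone less than 3 weeks prior to the start of study medication".
- Exclusion 9: "Use of systemic glucocorticoid (e.g., prednisone, dexamethasone) within 14 days prior to the start of study medication".
- Exclusion 11 covers herbs: "Prior use of any herbal products known to decrease PSA levels (e.g., PC-SPES or saw palmetto) within 30 days prior", counted back from the first dose.
- Exclusion 2 needs no interval, because it bars the treatments outright: "Prior chemotherapy and experimental therapy (PARP or checkpoint inhibitor").

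Once treatment starts, Section 8.6.2 prohibits "Any concurrent chemotherapy, radiotherapy, hormonal therapy (AR antagonists.), or immunotherapy". Section 8.6.1 adds that "subjects requiring palliative radiation anti-cancer therapy will be removed from the study", while LHRH therapy already in use must continue.

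Section 3.1 places nilutamide, flutamide and bicalutamide in the same class as enzalutamide. It says of GT0918 that "it can maintain a pure role of an antagonist because it does not activate the AR of CRPC cells compared to bicalutamide". The baseline table in Section 13.3 has rows for one, two, three, and four or more lines of prior hormonal therapy.

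Section 13.4 compares PSA at Week 12 with the study-entry value and also takes the maximum change at any time. The Synopsis states that there is no reference product.

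**The concern.** The intervals for enzalutamide, abiraterone, glucocorticoids and herbs serve to stop an earlier treatment from moving the outcome after GT0918 begins. The same reasoning applies to another AR antagonist or to radiotherapy, yet the list requires 30 days off saw palmetto and no time off bicalutamide.

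If a subject reaches Day 1 while PSA or lesions are still responding to an earlier treatment, or to its withdrawal, the change from baseline mixes that effect with the effect of GT0918. The error can go either way. A delayed benefit of radiotherapy, or a PSA fall after stopping a drug that stimulates the receptor, would flatter GT0918. A drug still holding PSA down at baseline would make GT0918 look worse. At stake are the within-arm estimates of activity that would inform later studies: PSA50, PSA change and objective response.

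**Working it through.** The plan states no figure on this point, so the check is mainly a comparison of the rules.

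**1. Rules before and after Day 1**

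| Treatment | Before Day 1 (Synopsis, 7.2) | From Day 1 (8.6.1, 8.6.2) |
|---|---|---|
| Enzalutamide, abiraterone | 3 weeks (exclusion 1) | Prohibited |
| Systemic glucocorticoids | 14 days (exclusion 9) | Prohibited |
| PSA-lowering herbs | 30 days (exclusion 11) | Prohibited |
| Chemotherapy, PARP or checkpoint inhibitors | Barred (exclusion 2) | Prohibited |
| Other AR antagonists | None | Prohibited |
| Other anticancer hormonal drugs | None | Prohibited |
| Radiotherapy | None | Prohibited; need for palliative radiation means removal |
| Immunotherapy outside exclusion 2 | None | Prohibited |
| LHRH therapy (mCRPC, unless orchiectomised) | Must be ongoing | Must continue |

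The gap is rows five to eight. No other section fills it. The last row needs no interval.

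**2. Who can enter.** Take a subject who progressed on enzalutamide, stopped it more than 3 weeks ago, and took bicalutamide until the day before Day 1. Inclusion 6 requires progression despite abiraterone or enzalutamide, but not that either was the most recent therapy. Exclusion 1 is satisfied, and Section 8.6.2 does not yet apply. The subject is eligible. So is one irradiated the day before Day 1.

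**3. How this reaches the endpoints.** PSA50 and PSA change use the study-entry value, and no untreated arm shows what would have happened without GT0918. Under Section 9.2.1 and footnote 3 of the Schedule of Assessments, the baseline scan may be up to 6 weeks old, so treatment given after that scan falls inside the measured lesion change. Section 13 describes no adjustment or sensitivity analysis for recent therapy.

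**4. Size per subject.** Arms have 30 subjects and prior-therapy groups within arms have 15 (2 × 30 = 4 × 15 = 60, consistent with the Synopsis and Section 13.1).

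- One responder in an arm: 1/30 = 3.3 points.
- One responder in a group: 1/15 = 6.7 points.

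For scale, an observed 1/30 has an exact 95% interval of 0.1% to 17.2%, and 3/30 (10.0%) has 2.1% to 26.5%.

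**5. Illustration under assumptions that are not in the documents.** Let w be the share of an arm recently exposed and r the share of those whose PSA falls by at least half for that reason. The expected number of misattributed responders is 30 × w × r, and the chance of at least one is 1 − (1 − wr)^30.

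- w = 10%, r = 10%: 0.3 responders, 1 point, 26% chance of at least one.
- w = 20%, r = 20%: 1.2 responders, 4 points, 71%.
- w = 30%, r = 30%: 2.7 responders, 9 points, 94%.

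This counts every such fall as an extra responder. Subjects who would have responded anyway would reduce the net effect.

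**The case against.** Several safeguards narrow the problem.

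- Entry requires documented progression. On the PSA route, a confirmatory value below the screening value triggers another test. This makes it harder to enter with PSA already falling. It does not cover entry by the RECIST or bone-scan routes, or a fall that begins after the earlier drug is stopped.
- The RECIST appendix usually treats irradiated lesions as non-measurable unless they have progressed. That limits the effect on target lesions but does nothing for PSA. The appendix also asks protocols to detail the conditions, and this one does not.
- Ketoconazole is on the Appendix 4 list, but exclusion 10 concerns co-administration and sets no interval.

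The evidence on frequency is thin. The table in Section 13.3 counts lines of therapy, not their timing, and it has a row for one prior chemotherapy line although exclusion 2 bars chemotherapy. Section 3.2.2 lists bicalutamide, radium 223 and sipuleucel T among treatments given to the phase I subjects, so such histories are foreseeable, but no rate follows.

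The mechanism is partly inference. Section 3.1 implies that bicalutamide can activate the receptor in CRPC cells; it does not say that stopping it lowers PSA. Section 13 also defers detail to an SAP that takes precedence, and no separate SAP text is in the documents, so a sensitivity analysis may be planned there.

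A reader might go further than the documents allow in four ways:

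- **That the dose comparison is biased.** Both arms share the same criteria and are randomised, so recent exposure is balanced on average.
- **That early adverse events are misattributed on a scale that undermines the safety objective.** Exclusion 3 (ongoing toxicity above grade 1), the screening blood-count limits, exclusion 13 on transfusion, and an AE definition limited to conditions that emerge or worsen all work against this.
- **That PSA50 is overstated by some stated proportion.** Any relative figure needs a true response rate, and the documents give none.
- **That the exclusions contradict Section 8.6.2.** One governs entry and the other concurrent use. This is an omission, not a conflict.

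**Conclusion.** The gap is real and appears in both copies of the criteria. As written, they admit subjects who stopped another AR antagonist or another anticancer hormonal drug, or who had radiotherapy or immunotherapy outside exclusion 2, the day before Day 1. The resulting change in PSA or lesions can count as GT0918 activity in PSA50, PSA change and objective response.

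The number affected is unknown, so the supportable statement of size is per subject: 3.3 points per arm and 6.7 points per 15-subject group for each misattributed responder. The range of 1 to 9 points rests wholly on assumed exposure and response rates of 10% to 30% each. The direction is not fixed.

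The affected endpoints are secondary and descriptive. The primary endpoint is dose selection on safety, tolerability and exposure, and neither it nor the randomised comparison is systematically affected. The point is worth correcting because the remedy is cheap and these endpoints have no other control.

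**What to change.** 1. **Eligibility.** In the Synopsis and Section 7.2, align the exclusions with Section 8.6.2. Give an interval before Day 1 to other AR antagonists, other anticancer hormonal drugs, radiotherapy, and immunotherapy not already barred by exclusion 2. Continuing LHRH therapy is exempt. The sponsor sets and justifies each length.
2. **Data.** Confirm that the eCRF records the last date of each such treatment at screening. Section 9.2.1 collects history and prior medication but does not expressly ask for stop dates.
3. **Analysis.** In Section 13.4, and in the SAP, flag subjects with any such treatment less than 21 days before Cycle 1 Day 1. This borrows exclusion 1's length for analysis only and is not a proposed eligibility interval. Report PSA50, PSA change and soft-tissue response with and without flagged subjects. The flag is fixed before dosing, so it does not select on outcome. It will miss treatment given between a baseline scan up to 42 days old and the 21-day limit, which should be noted beside the soft-tissue result.

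The cost is wording in two places, a check of the eCRF, one extra table, and a slightly later start for some subjects. Enrolment began in 2Q2019 and this version is dated March 2021, so the eligibility change may reach few subjects. The analysis flag can cover everyone enrolled, provided the dates exist or can be recovered from source records.
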